10.5 Appendix 5: Liver safety monitoring

To ensure participant safety and enhance reliability in determining the hepatotoxic potential of an investigational drug, a standardized process for identification, monitoring and evaluation of liver events has to be followed.

Please refer to [Table 10-1](#) in Appendix 5 for complete definitions of liver laboratory triggers.

Once a participant is exposed to study treatment, every liver event defined in [Table 10-1](#) should be followed up by the Investigator or designated personnel at the trial site, as summarized below. Since deterioration of PAH may result in increases of liver values it should be checked if an increase of liver values might be secondary to a deterioration of right heart failure. Liver chemistry tests (i.e. ALT, AST, TBL, PT/INR, ALP and G-GT) to confirm elevation. Increased liver values considered secondary to deterioration of right heart function are not considered liver events

- Liver chemistry repeats will be performed using the central laboratory. If results will not be available from the central laboratory, then the repeats can also be performed at a local laboratory to monitor the safety of the participant. If a liver event is subsequently reported, any local liver chemistry tests previously conducted that are associated with this event should have results recorded on the appropriate CRF.
- If the initial elevation is confirmed, close observation of the participant will be initiated, including consideration of treatment interruption if deemed appropriate.
- Discontinuation of the investigational drug (refer to the Discontinuation of study treatment [Section 7.1](#)), if appropriate
- Hospitalization of the participant if appropriate
- Causality assessment of the liver event
- Thorough follow-up of the liver event should include, as per the investigator's discretion to allow for a causality assessment: serology tests, imaging and pathology assessments, hepatologist's consultancy; obtaining more detailed history of symptoms and prior or concurrent diseases, history of concomitant drug use, exclusion of underlying liver disease.

All follow-up information and procedures performed must be recorded as appropriate in the eCRF.

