10.5.1 Liver event and laboratory trigger definitions & follow-up requirements

Table 10-1 Liver event and laboratory trigger definitions

	Definition/ threshold
Liver laboratory triggers If ALT, AST and total bilirubin normal at baseline:	
 • ALT or AST $> 5 \times$ ULN • ALP $> 2 \times$ ULN (in the absence of known bone pathology) • Total bilirubin $> 3 \times$ ULN (in the absence of known Gilbert syndrome) • ALT or AST $> 3 \times$ ULN and INR > 1.5 • Potential Hy's Law cases (defined as ALT or AST $> 3 \times$ ULN and Total bilirubin $> 2 \times$ ULN [mainly conjugated fraction] without notable increase in ALP to $> 2 \times$ ULN) • Any clinical event of jaundice (or equivalent term) • ALT or AST $> 3 \times$ ULN accompanied by (general) malaise, fatigue, abdominal pain, nausea, or vomiting, or rash with eosinophilia • Any adverse event potentially indicative of a liver toxicity
If ALT or AST abnormal at baseline:	
 • ALT or AST $> 3 \times$ baseline or > 300 U/L (whichever occurs first)

Notify Novartis study lead and medical lead of any finding of a liver event identified not explained by PAH worsening for further follow-up assessments.

Table 10-2 Follow up requirements for liver laboratory triggers - ALT, AST, TBL

	ALT	TBL	Liver Symptoms	Action
ALT increase without bilirubin increase:				
	If normal at baseline: ALT $> 3 \times$ ULN	Normal For participants with Gilbert's syndrome: No change in baseline TBL	None	
 • No change to study treatment • Measure ALT, AST, ALP, GGT, TBIL, INR, albumin, CK, and GLDH in 48-72 hours. • Follow-up for symptoms.
	If elevated at baseline: ALT $> 2 \times$ baseline or > 300 U/L (whichever occurs first)			

	ALT	TBL	Liver Symptoms	Action
	If normal at baseline: ALT > 5 x ULN for more than two weeks	Normal For participants with Gilbert's syndrome: No change in baseline TBL	None	
 • Interrupt study treatment • Measure ALT, AST, ALP, GGT, TBIL, INR, albumin, CK, and GLDH in 48-72 hours. • Follow-up for symptoms. • Initiate close monitoring and workup for competing etiologies. • Study treatment can be restarted only if another etiology is identified and liver enzymes return to baseline.
	If elevated at baseline: ALT > 3 x baseline or > 300 U/L (whichever occurs first) for more than two weeks			
	If normal at baseline: ALT > 8 x ULN	Normal	None	
ALT increase with bilirubin increase:				

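### For isolated ALT elevation, the only interruption row in Table 10-2 without a waiting period covers normal-baseline participants only; those with elevated baseline ALT stay under an unbounded no-change row for two weeks

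*Protocol*

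**What the plan says.** Protocol section 10.5.1, Table 10-2, deals first with ALT increases where bilirubin is normal and there are no liver symptoms.

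- **First row.** Normal baseline: ALT above 3 x ULN. Elevated baseline: ALT above 2 x "baseline or > 300 U/L (whichever occurs first"). The action is "No change to study treatment", with repeat tests in 48-72 hours and symptom follow-up. Neither criterion has an upper limit.
- **Second row.** "If normal at baseline: ALT > 5 x ULN for more than two weeks", paired with "If elevated at baseline: ALT > 3 x baseline or > 300 U/L (whichever occurs first) for more than two weeks". The action is "Interrupt study treatment", with repeat tests and a work-up.
- **Third row.** "If normal at baseline: ALT > 8 x ULN", with no duration condition and no elevated-baseline partner. Its action cell is blank in the text available.

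The later rows, for ALT with raised bilirubin or INR and for ALT with liver symptoms, give criteria for both baseline groups without a waiting period. Their action cells are blank in the same way.

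The general text of section 10.5 calls for close observation once an elevation is confirmed, "including consideration of treatment interruption if deemed appropriate". Section 6.5 says that study treatment may not be interrupted. Section 7.1 sends liver events to Appendix 5 for guidance on discontinuation.

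**The concern.** A participant whose ALT was already elevated at baseline has no row corresponding to the third one. For isolated ALT, the only interruption criterion open to that participant requires more than two weeks' duration. Until then the specific instruction is no change, however high the value. A normal-baseline participant at the same or a lower ALT reaches the interruption block at once.

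Long-term safety is the primary objective of this extension, and former placebo participants receive LTP001 here for the first time. Section 10.5 presents the liver process as standardized and obligatory, so sites can be expected to act on the table as printed. Section 6.5 adds a second difficulty: a site that interrupts early by judgement would act against both a no-change row and a general ban on interruption.

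**Working it through.** The plan states no figure to reproduce. The check applies the isolated-ALT rows of Table 10-2 as a decision rule (bilirubin and INR normal, no symptoms).

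**Inputs from the protocol.** Normal baseline: 3 x ULN (no change), 5 x ULN for more than two weeks (interrupt), 8 x ULN (interrupt, by the merged-cell reading). Elevated baseline: 2 x baseline or 300 U/L (no change), 3 x baseline or 300 U/L for more than two weeks (interrupt).

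**Assumptions.** The documents give no ULN for ALT in U/L. I take 40 U/L, with a range of 30 to 55, and an elevated baseline of 1.5 x ULN.

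**Example at ULN 40 U/L.**

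- Normal baseline: 8 x 40 = 320 U/L. An ALT of 321 meets the third row on day 0.
- Elevated baseline: 1.5 x 40 = 60 U/L. The no-change row starts above the lower of 2 x 60 = 120 and 300, so above 120 U/L. The two-week row starts above the lower of 3 x 60 = 180 and 300, so above 180 U/L.
- ALT 600 in that participant is 600/40 = 15 x ULN and 600/60 = 10 x baseline. It falls under no change on day 0 and still on day 14, and meets the interruption row only after day 14.

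**Across the assumed range**, at ALT = 10 x ULN:

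| ULN (U/L) | 8 x ULN | Baseline 1.5 x ULN | ALT 10 x ULN | Normal baseline, day 0 | Elevated baseline, days 0-14 | Elevated baseline, day 15 |
|---|---|---|---|---|---|---|
| 30 | 240 | 45 | 300 | interrupt | no change | interrupt |
| 35 | 280 | 52.5 | 350 | interrupt | no change | interrupt |
| 40 | 320 | 60 | 400 | interrupt | no change | interrupt |
| 45 | 360 | 67.5 | 450 | interrupt | no change | interrupt |
| 50 | 400 | 75 | 500 | interrupt | no change | interrupt |
| 55 | 440 | 82.5 | 550 | interrupt | no change | interrupt |

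At 10 x ULN the ratio to baseline is 10/1.5 = 6.7 throughout. The pattern is the same just above 8 x ULN and at 20 x ULN (20/1.5 = 13.3 x baseline). The assumed ULN moves the level at which the two groups part, but not the fact that they do.

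**The case against.** The strongest reply is that Table 10-2 is not the only safeguard.

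- The example participant meets the Table 10-1 trigger for abnormal baseline (above 3 x baseline or 300 U/L) without any wait. That brings sponsor notification and the section 10.5 follow-up, unless the rise is put down to PAH worsening or right heart deterioration.
- The no-change row itself requires repeat tests in 48-72 hours.
- Section 10.5 allows interruption to be considered, section 7.1 requires stopping where continuation might be a safety risk, and section 8 asks for immediate concerns to be discussed with the sponsor.

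This stands as mitigation. A reader might infer that the protocol keeps the elevated-baseline participant on drug whatever happens; it does not. But none of these provisions sets an ALT level for interruption, and they sit beside a specific row that says no change.

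Other limits also stand:

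- A reader might take the third row to be the only isolated-ALT row without a duration condition. The first row has none either; the third is the only one in the interruption block.
- A reader might take "Since deterioration of PAH may result in increases of liver values" to mean that elevated baselines are expected. It concerns worsening on study. Neither document says how many of the approximately 40 participants have elevated baseline ALT, and the parent study's eligibility limits are not visible.
- The table is not uniformly laxer for elevated baselines. With ULN 40 and baseline 60, the sustained criterion is 3 x 60 = 180 U/L against 5 x 40 = 200 U/L for normal baseline. A normal-baseline participant between 5 and 8 x ULN also waits two weeks.
- The blank action cell is an inference. The bilirubin and symptom rows are blank in the same way, which makes the merged reading the sensible one, but a line lost in text extraction cannot be wholly excluded.
- A reader might infer damage to a planned analysis. The SAP plans no analysis of liver-related treatment actions by baseline ALT and no subgroups, so the issue is participant safety and consistent conduct.

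**Conclusion.** The gap is real and narrow. For isolated ALT elevation, with normal bilirubin and INR and no symptoms, Table 10-2 has no counterpart to its 8 x ULN row for participants with elevated baseline ALT. They remain in a no-change row with no upper limit until more than two weeks have passed. The table can therefore be less cautious for them at the same or a higher absolute ALT.

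The conclusion rests on reading the blank action cell as part of the interruption block. The U/L figures rest on an assumed ULN, but the asymmetry held at every ULN tried from 30 to 55 U/L. The number of participants affected is unknown and could be very small or zero. If the omission is deliberate, the protocol gives no reason for it.

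**What to change.** Reconcile the Table 10-2 rows so that the protocol states what applies to elevated-baseline participants in the situation that the 8 x ULN row covers, and how that relates to the overlapping no-change row. Confirm the action that belongs to the blank cell. In the same edit, reconcile the interruption instructions in Tables 10-2 and 10-3 with section 6.5. The sponsor's hepatic safety experts decide the content; no threshold or action is proposed here.

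The cost is a table edit and a cross-reference in a protocol amendment, with the usual ethics committee approval and, where required, health authority approval. It need not add tests. Depending on what the experts decide, a few more participants may meet a treatment-action row.

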10.6 Appendix 6: Renal safety monitoring

10.6.1 Specific Renal Alert Criteria and Actions and Event Follow-up

Renal safety parameters will be checked at all visits. Careful monitoring of deterioration of renal function or of pathologic changes in the urinalysis is required. The below definitions mandate to classify a renal parameter deviation as a renal event.

Table 10-4 Specific renal alert criteria and actions

Serum Event	
Serum creatinine increase > 25% fold compared to baseline	Follow up within 1-2 days (Refer to Table 8-2)
Urine Event	
New onset dipstick proteinuria $\geq 3+$ OR New onset dipstick hematuria $\geq 3+$ (after excluding menstruation, urinary tract infection, extreme exercise, or trauma)	Follow up within 2-5 days (Refer to Table 8-2)
For all renal events:	
Document contributing factors in the eCRF: co-medication, other co-morbid conditions, and additional diagnostic procedures performed	
Monitor subject regularly (frequency at investigator's discretion) until either:	
Event resolution: sCr within 20% of baseline or	
Event stabilization: sCr level with $\pm 20\%$ variability over last 2 months	
Further recommendations on the follow-up for renal events can be found in the investigator portal (Follow-up for renal events document).	

11 References

References are available upon request

Hemnes AR, Humbert M (2017) Pathobiology of pulmonary arterial hypertension: understanding the roads less travelled. *Eur Respir Rev*; 26(146):170093.

5.1.3	Concomitant medication date imputation	21
5.2	AEs coding/grading	22
5.3	Laboratory parameters derivations	22
5.4	Statistical models	23
5.5	Rule of exclusion criteria of analysis sets.....	23
6	Reference	23

List of tables

Table 1-1	Objectives and related endpoints	7
Table 2-1	Protocol deviation codes and analysis sets.....	10
Table 2-2	Clinical notable criteria for QTcF (Fridericia's formula).....	13
Table 5-1	Directions of interest for worst case value for laboratory parameters	22

List of figures

Figure 1-1	Study Schema.....	7
------------	-------------------	---

List of abbreviations

AE	Adverse Event
BP	Bood pressure
CCI	[REDACTED]
CRF	Case Report Form
CSR	Clinical Study Report
DBL	Database lock
DMS	Document Management System
ECG	Electrocardiogram
EOS	End of Study
EOT	End of treatment
FAC	fractional area change
IA	Interim Analyses
LLOQ	Lower limit f quantification
MedDRA	Medical Dictionary for Drug Regulatory Affairs
CCI	[REDACTED]
NT-proBNP	the N-terminal fragment of the prohormone B-type natriuetic peptide
OLE	the open label extension
PAH	pulmonary arterial hypertension
PK	Pharmacokinetics
CCI	[REDACTED]
CCI	[REDACTED]
CCI	[REDACTED]
PRO	Patient-reported Outcomes
RAP	Reporting & Analysis Process
RV S'	peak velocity of excursion
RVF	right ventricular function
SAP	Statistical Analysis Plan
SAS	Statistical Analysis System
SMQ	Standardized MedDRA Query
TAPSE	tricuspid annular plane systolic excursion
TASV	tricuspid annular systolic velocity
TFLs	Tables, Figures, Listings
TS	Trial Statistician
TP	Trial Programmer
TTCW	Time to Clinical Worsening
ULOQ	Upper limit of quantification

1 Introduction

The Reporting and Analysis documents contain detailed information to aid the production of Statistics & Programming input into the Clinical Study Report (CSR) for trial “CLTP001A12201E1”.

This Statistical Analysis Plan (SAP) has been developed in accordance with Clinical Trial Protocol CLTP001A12201E1 (Protocol Version 01, released on 30-Jan-2023), and describes the implementation of the statistical analysis planned in the protocol.

1.1 Study design

This is a non-randomized, open-label extension study over 52 weeks with LTP001 without a control treatment arm. Participants will be presented the opportunity to consider the extension study at the End of Treatment (EOT) visit (Week 25) of the parent study CLTP001A12201. The investigator will assess if the participant will continue by verifying that the participant has completed the parent study as planned. Moreover, at the EOT the investigator will determine the eligibility for the extension study (i.e. that none of the treatment discontinuation criteria were met and that the assessments at the EOT of the parent efficacy study were completed according to the parent protocol). The patient may directly continue into the extension study. If the patient does not directly continue in the extension study, the time between the end of treatment assessments in the parent study and the enrollment in the extension study i.e. during the transition period should be kept to a minimum (it should not exceed 14 days).

In case of a direct transition into the extension study after the end of treatment visit in the parent study, as not all assessment results will be available (e.g. the central lab assessments) at the same day the investigator will re-assess/reconfirm the eligibility as soon as outstanding results are received.

The safety and efficacy of LTP001 will be checked at the following visits: Weeks 5, 13, 26, 39 and 52, as specified in the Assessment Schedule. Safety and tolerability assessments will take place at each visit. RHC will be performed at week 26 and 6MWT and echocardiography will be assessed at Weeks 26 and 52. PAH-SYMPACT and emPHasis-10 will be collected for 7 day intervals with the seventh day of collection occurring within the allotted visit window for all Treatment visits (Weeks 5, 13, 26, 39 and 52). Participants will have safety follow-up phone calls at Weeks 9 and 17, and may be invited for safety assessment at site if deemed necessary. The PI may exercise their discretion in which safety assessments are required at these optional safety follow-up visits. Following the end of treatment period, participants will have one safety follow-up phone call approximately 30 days after the end of treatment visit at Week 52. The duration of the extension study is currently restricted to 52 weeks, but the study may be prolonged (via an amendment to the protocol) if the LTP001 development program in PAH continues and the benefit/risk assessment remains favorable for the patient population studied. The safety and efficacy profile of LTP001 that is observed in this extension study as well as the parent study, CLTP001A12201, will determine continuation of the extension study.

Please refer to [Figure 1-1](#) for study design figure.

Figure 1-1 Study Schema

1.2 Study objectives, endpoints and estimands

Table 1-1 Objectives and related endpoints

Objective(s)	Endpoint(s)
Primary objective(s)	Endpoint(s) for primary objective(s)

To assess the long term safety of LTP001 in participants with pulmonary arterial hypertension (PAH).	
AEs, SAEs, vital signs, ECGs, safety laboratory measurements
Secondary objective(s)	Endpoint(s) for secondary objective(s)

To evaluate the effect of LTP001 on hemodynamic parameters derived from RHC including PVR, RA pressures, mean PA pressure, PCWP, CO, SVR.To assess the effect of LTP001 on the 6MWDTo assess the effect of LTP001 on measurements of right ventricular function (RVF) in participants with PAH	
Change from baseline at week 26 for each parameterChange in 6MWD from baseline over timeChange from baseline in tricuspid annular plane systolic excursion (TAPSE) by echocardiography Change from baseline in tricuspid annular systolic velocity (TASV) by echocardiography Change from baseline of peak velocity of excursion (RV S') by echocardiography

Objective(s)	Endpoint(s)

• To assess the impact of LTP001 on patient reported outcomes (PRO) in participants with PAH.• To assess the impact of LTP001 on Time to Clinical Worsening (TTCW) in participants with PAH.• To assess the impact of LTP001 on the N-terminal fragment of the prohormone B-type natriuetic peptide (NT-proBNP).	
Change from baseline in fractional area change (FAC) by echocardiography
 
• Change from baseline in EmPHasis-10 and PAH-SYMPACT• Death• Hospital stay (≥ 24 h) due to worsening of PAH. Worsening of PAH is defined by the following right heart failure related signs and symptoms: syncope or near syncope, cyanosis, increase of breathlessness, clinically relevant deterioration of exercise capacity, decrease of oxygen saturation, increased peripheral edema, hepatomegaly, and ascites• Worsening of PAH resulting in need for lung transplantation or balloon atrial septostomy• Initiation of parenteral prostanoïd therapy, chronic oxygen therapy, or any other PAH-specific therapies or need for increase of diuretics for more than 4 weeks due to worsening of PAH• Disease progression (switch in modified New York Heart Association/WHO FC by at least one grade)• Significant drop in 6MWD (15% from baseline or more) due to PAH-worsening• N-terminal fragment of the prohormone B-type natriuetic peptide

Exploratory objective(s)	Endpoint(s) for exploratory objective(s)
CCI	

1.2.1 Primary estimand(s)

Not applicable

2 Statistical methods

A Clinical Study Report (CSR) will be prepared following the completion of the study. Any data analysis carried out independently by the investigator should be submitted to Novartis before publication or presentation.

2.1 Data analysis general information

The final CSR analysis will be performed by Novartis Trial Statistician (TS) and Trial Programmer (TP). SAS version 9.4 or higher (SAS Institute, Cary NC) or later software will be used to perform all data analyses and to generate tables, figures, and listings.

Two change from baseline values will be reported for all the analyzed parameters planed in this document for this study:

- Change from baseline of the parent study (LTP001A12201, prior to the treatment start on Day 1)
- Change from baseline of the current extension study (LTP001A12201E1, parent study week 25)

The comparisons of these two change from baseline values and the treatment group difference within each change from baseline value will be reported.

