2.1.1 General definitions

Investigational treatment will be LTP001.

Date of first administration of study treatment (Day 1) will be defined as the date of the first actual administration of LTP001.

Date of last administration of study treatment will be defined as the date of the last actual administration of LTP001.

Two *Baselines* will be defined as the following:

Baseline of the Parent study: the Day 1 assessment of study LTP001A12201. If this datum is not available, the last pre-dosing assessment will be considered.

Baseline of the Extension study: Week 25 visit from LTP001A12201. If this datum is not available, the last pre-dosing assessment for this study (LTP001A12201E1) will be considered. *Study day* will be defined as the number of days since the date of first dose of study treatment (LTP001 or placebo). The date of first dose of study treatment will be defined as *Day 1* and the day prior to first dose of will be defined as *Day -1*. Therefore, for a particular date, study day will be calculated as follows:

for dates on or after the date of first dose of study treatment,

Study day = Assessment date – Date of first dose administration + 1

The on-treatment period lasts from the date of first administration of study treatment to the End of Study (EOS) visit or the date of last randomized dose if EOS visit is not available. The EOS visit is a follow-up visit that is approximately 30 days after the date of the last actual administration of investigational treatment. For participants who will be enrolled into the open label extension (OLE) study, their EOS visits will be skipped.

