2.6.1.1 Efficacy and/or pharmacodynamic endpoints(s)

All analyses will be conducted using PD analysis set.

Change from baseline for efficacy endpoints will be descriptively summarized by visit/time for treatment group assigned in the parent study, and overall. Two baseline measurements will be generated as per [Section 2.1.1](#). Graphs (e.g., spaghetti plot) will be provided to show individual time courses of parameters for the extension study together with the parent study.

Additionally, two changes from baseline values for efficacy endpoints will be descriptively summarized by visit/time for treatment group assigned in the parent study, and overall with the following comparisons:

- a) Short-term (change from baseline of extension study) vs. long-term (change from baseline of the parent study) treatment effect (For both treatment and placebo groups assigned in the parent study).
- b) the treatment group difference (assigned in the parent study) within each change from baseline value.

6MWD

This measures how many meters a person can walk in 6 minutes. It includes total distance walked (6MWD), the number and duration of any stops in 6 minutes. Test performed at baseline and at visits on Day 176 and 358 will be used for analysis.

Descriptive statistics (N, mean, SD, CV% mean, geometric mean, CV% geometric mean, median, min, and max) summarizing 6MWD parameters and their changes from baseline will be summarized by visit/time for treatment group assigned in the parent study and overall.

Panels of individual spaghetti plots over time/visit for treatment group assigned in the parent study and overall for each 6MWD parameter will be provided.

All 6MWD parameters will be listed by participant, and visit and if ranges are available, abnormalities will be flagged.

RHC

The RHC is performed to assess several hemodynamic parameters when the patient is in a stable hemodynamic rest state (as demonstrated by three consecutive cardiac output measurements with 10% of each other). The measurement is taken at baseline and at visit on Day 176. The assessed hemodynamic parameters include:

- PVR
- right atrial (RA) pressure
- mean pulmonary artery pressure (mPAP)
- pulmonary capillary wedge pressure (PCWP)
- systolic and diastolic blood pressure (RV pressures)
- heart rate (HR)
- cardiac output (CO)
- systemic vascular resistance (SVR)
- mixed venous blood gas measurement

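### SAP item (a) sets two changes from the same extension value against each other as short-term and long-term effect; any mean difference between them is only the gap between the two baselines

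*SAP*

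**What the plan says.** SAP 2.1 defines two changes for every analysed parameter: "Change from baseline of the parent study (LTP001A12201, prior to the treatment start on Day 1" and "Change from baseline of the current extension study (LTP001A12201E1, parent study week 25". It continues: "The comparisons of these two change from baseline values and the treatment group difference within each change from baseline value will be reported".

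SAP 2.1.1 fixes the reference values: "Baseline of the Parent study: the Day 1 assessment of study LTP001A12201" and "Baseline of the Extension study: Week 25 visit from LTP001A12201". Each has a fallback. For the extension baseline it reads: "If this datum is not available, the last pre-dosing assessment for this study (LTP001A12201E1) will be considered".

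SAP 2.6.1.1 gives the comparison its purpose for efficacy endpoints. Item (a) is "Short-term (change from baseline of extension study) vs. long-term (change from baseline of the parent study) treatment effect (For both treatment and placebo groups", by visit. Item (b) is the difference between parent-study arms within each change.

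The SAP nowhere says whether comparison means a difference, a test or a side-by-side display; SAP 2.6.2 says only that most of these analyses are descriptive. The end of SAP 2.6.1.1 separately keeps the mixed-baseline summary of Protocol 9.4.1: the parent-LTP001 arm is measured from the parent baseline, and those switching from placebo from the extension baseline. Protocol 9.4.1 does not plan a comparison of the two changes, and SAP section 4 lists no departures from the protocol.

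**The concern.** Below, *continuers* had LTP001 in the parent study and *switchers* had placebo.

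Protocol 2.3 says what the extension is meant to show: the Week 26 catheterization gives a one-year effect in continuers and a six-month effect in switchers. That sets one arm beside the other. Item (a) instead sets two baselines against each other within one arm, at one visit, with the same follow-up value in both changes.

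If the difference between the two changes is tabulated as means, it cannot respond to what happens in the extension. A stable figure from Week 26 to Week 52 could be read as a durable effect, and a moving figure as gain or loss, when it reflects only who was measured. For mean PVR, which has one scheduled extension visit, the contrast repeats parent-study information. In switchers it is change on placebo reported under a treatment-effect label.

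**Working it through.** **Inputs.** Y = value at an extension visit (6MWD and echocardiography on Days 176 and 358, RHC on Day 176; SAP 2.6.1.1). B1 = parent baseline and B2 = extension baseline (SAP 2.1.1). The plan states no effect size, SD or sample size to reproduce.

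**Identity.**
- Long-term change: L = Y − B1
- Short-term change: S = Y − B2
- L − S = (Y − B1) − (Y − B2) = B2 − B1

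Y drops out for each participant, and therefore for means when the same participants contribute to both changes. B2 − B1 is normally the change from parent Day 1 to parent Week 25. If Week 25 is missing, B2 is the last pre-dose value; Y still cancels, but the result is no longer strictly the Week 25 change.

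**Numerical check on assumed data.** Assumptions, not trial figures: 20 participants per arm, 6MWD baseline mean 400 m and SD 80 m, SD of changes 40 m, and true parent Week 25 change of 30 m (continuers) or 0 m (switchers). Three very different extension courses were imposed. Cells show mean L, mean S, then L − S, in metres.

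| True extension change, Week 26 / Week 52 | Continuers, Week 26 | Continuers, Week 52 | Switchers, Week 26 | Switchers, Week 52 |
|---|---|---|---|---|
| −60 / −60 | −37.4, −66.1, **28.7** | −36.9, −65.6, **28.7** | −69.0, −71.3, **2.3** | −65.6, −67.9, **2.3** |
| 0 / 0 | 22.6, −6.1, **28.7** | 23.1, −5.6, **28.7** | −9.0, −11.3, **2.3** | −5.6, −7.9, **2.3** |
| +60 / +100 | 82.6, 53.9, **28.7** | 123.1, 94.4, **28.7** | 51.0, 48.7, **2.3** | 94.4, 92.1, **2.3** |

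The differences equal the simulated mean parent Week 25 changes (28.725 and 2.319 m). The paired t-statistics, 2.651 and 0.315, are also the same in every row and at both visits.

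**Missing data.** With 30% missing at Week 52 (third row's course), L − S at Week 52 becomes 133.3 − 97.8 = 35.5 m in continuers and 84.3 − 87.7 = −3.4 m in switchers. These are the parent Week 25 changes of those still measured. Nobody's response changed.

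**Medians.** A difference of medians need not cancel. In continuers it was 26.5 m at Week 26 and 32.2 m at Week 52, against a median parent change of 32.3 m. It was still identical in all three rows, because shifting everyone's Y by the same amount shifts both medians equally.

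**Labels, if the two changes are only shown side by side at Week 26.**

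| | From parent baseline (called long-term) | From extension baseline (called short-term) |
|---|---|---|
| Continuers | About one year on LTP001: label fits | Second half of that year, already on drug: maintenance, not a short-term effect |
| Switchers | About 25 weeks on placebo, then about 25 on LTP001: not a long-term effect | First 25 weeks or so on LTP001: label fits |

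By Week 52 the switchers' change from the extension baseline itself spans about a year on drug.

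**What does not cancel.** In item (b), each group difference is formed from the Y values of two different arms. The mixed-baseline summary also combines different people. Both keep the extension data.

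**The case against.** The strongest reply is that subtraction is assumed. The SAP describes descriptive summaries and names no difference statistic, test or model for item (a). In a side-by-side table each column contains Y: continuers at Week 26 would show −37.4 and −66.1 m under the first course above and 82.6 and 53.9 m under the third. Nobody would miss the deterioration. This stands, and the cancellation is therefore limited to a derived contrast. It does not rescue the labels.

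A reader might infer more than the documents support:

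- *That the difference equals the Week 25 change exactly, at every visit.* It does so for individual values and means among those measured, when Week 25 is available. The fallback, missing data and medians each break strict equality.
- *That the plan would hide a complete loss of benefit, or makes no use of extension data.* It does not. Both changes are reported by visit, with item (b), the mixed-baseline summary and individual plots spanning both studies.
- *That the informative analyses are all absent.* Continuers' change from Week 25 and switchers' change over the extension are already planned. What is missing is the switchers' on-drug change beside their on-placebo change, and a comparison of the first 25 weeks or so on drug in the two arms. The mixed-baseline summary at Week 26 sets about one year in continuers beside about six months in switchers, so it supplies neither.

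These are also secondary, descriptive endpoints in an uncontrolled safety extension, and no decision rule rests on item (a). That limits the importance of the point but does not make item (a) correct.

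**Conclusion.** The point holds in this form. Any contrast of individual values or means between the two changes reduces to extension baseline minus parent baseline. It carries no extension outcome, can move between visits only through who is measured, and in switchers is change on placebo. If nothing is subtracted, the short-term and long-term labels are still wrong for continuers' change from Week 25 and switchers' change from Day 1.

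The identity rests on two conditions: absolute changes, as the SAP specifies, and the same participants in both columns. It does not depend on the simulated values; the metre figures are illustrative and say nothing about the size of any effect in this trial. The correction should be made, because the analysis as labelled does not answer its question. The consequence is confined to the interpretation of secondary descriptive results.

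**What to change.** 1. In SAP 2.1, remove the comparison of the two changes and keep the group difference within each change.
2. In SAP 2.6.1.1, delete item (a). State that the difference between the two columns is not to be interpreted as durability.
3. Label the planned change from the extension baseline as maintenance of effect in continuers, and as change over the first weeks on LTP001 in switchers, giving the time on drug at each visit.
4. Add two descriptive contrasts:
   - within switchers, change from parent Week 25 to extension Week 26 beside change from parent Day 1 to Week 25;
   - continuers' parent-study Week 25 change beside switchers' extension Week 26 change.
5. Report the number of participants contributing to each contrast, and record the additions in SAP section 4, since Protocol 9.4.1 does not contain them.

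The cost is SAP wording and two further summaries from data already collected. The downside is small but should be stated with the results: both contrasts set open-label change against double-blind change, so expectation and time are mixed with drug effect, and both use only participants with the values needed. They remain descriptive.
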